Protocol Number/ Title	Protocol Number WVU010516 Use of Response-Adapted Hypofractionated Radiation Therapy to Potentiate the Systemic Immune Response to Checkpoint Inhibitors in Non-Small Cell Lung Cancer
Study Phase	Phase II
Brief Background/ Rationale	Preclinical data suggest that radiation therapy may be uniquely suited to combine with immune checkpoint inhibitors, since radiation can disrupt a tumor's physical barriers to T-cell infiltration and augment antigen presentation, thus serving as an "in situ personalized vaccine" to activate the immune system and potentially enhance the systemic response. However, the optimal way to combine immune checkpoint inhibitors and radiation therapy is poorly understood, and there is little prospective data evaluating the efficacy in patients. The rationale for this study is to determine the safety and efficacy of combined immune checkpoint inhibitors and radiation therapy in metastatic non-small cell lung cancer patients.
Primary Objective	Primary Endpoint: Best overall response rate (ORR) (complete and partial), measured on follow-up imaging as per immune-related Response Criteria (irRC) after initiation of therapy.
Secondary Objective(s)	Secondary Endpoint(s): Progression-free survival (PFS), overall survival (OS), toxicity using CTCAE v4.0, quality of life using FACT-L.
Exploratory Objective(s)	Exploratory Endpoint(s): Univariate and multivariate analysis will be used to correlate the presence of response with radiotherapy variables (biologic effective dose, number of fractions, duration of radiotherapy, sequence of radiation and immune therapy), tumor variables (irradiated tumor site, size, histology, local response, extent of prior chemotherapy use), and patient variables (age, smoking status, and biologic correlates).
Correlative Objective(s)	Correlative Endpoint(s): In consenting patients peripheral blood samples will be collected before initiation of radiation therapy, at the time of the first follow-up imaging study, and for any change in response status on reimaging to assess levels of circulating CD4+, CD8+ and Treg T-cell subsets, as well as iNOS+/CD80+ macrophages. We will also assess immune cell trafficking by determining levels of circulating cytokines (HGF, TGF- β) and chemokines (CCL2 for M1 macrophages, and CXCL9, CXCL10, and CXCL11 for T-cells). We will also determine changes of the circulating T-cells immune-repertoire (i-repertoire) by performing next generation sequencing of the CDR3 region of the T-cell receptor (TCR).
Sample Size	33
Disease Sites/ Conditions	Stage IV NSCLC (ICD-10 code C34.90)
Interventions	Radiation therapy, 3-5 fraction course over 3-21 days Immune therapy per standard of care physician's discretion

ABBREVIATIONS

3DCRT	3-Dimensional Conformal Radiation Therapy	irAE	Immune-related Adverse Events
BED	Biologically Effective Dose	irRC	Immune-related Response Criteria
CCL	Chemokine (C-C Motif) Ligand	ITV	Internal Target Volume
CD4	Cluster of Differentiation 4	MBRCC	Mary Babb Randolph Cancer Center
CD8	Cluster of Differentiation 8	MDSC	Myeloid Derived Suppressor Cell
CRF	Case Report Form	MHC	Major Histocompatibility Complex
CRP	C-reactive Protein	MRI	Magnetic Resonance Imaging
CT	Computed Tomography	MV	Megavoltage
CTCAE	Common Terminology Criteria for Adverse Events	NGS	Next Generation Sequencing
CTLA-4	Cytotoxic T-lymphocyte Antigen 4	NSCLC	Non-Small Cell Lung Cancer
CTRU	Clinical Trials Research Unit	OAR	Organ-at-Risk
CTV	Clinical Target Volume	ORR	Overall Response Rate
CXCL	Chemokine (C-X-C motif) ligand	OS	Overall Survival
DSTC	Data Safety Toxicity Committee	PD-1	Programmed Death Receptor 1
ESR	Erythrocyte Sedimentation Rate	PD-L1	Programmed Death-Ligand 1
ECOG	Eastern Cooperative Oncology Group	PERCIST	PET Response Criteria in Solid Tumors
FACIT	Functional Assessment of Chronic Illness Therapy	PET	Positron Emission Tomography
FACT	Functional Assessment of Cancer Therapy	PFS	Progression Free Survival
FDA	Food and Drug Administration	PRMC	Protocol Review and Monitoring Committee
Gy	Gray	PTV	Planning Target Volume
GTV	Gross Tumor Volume	QOL	Quality of Life
HGF	Hepatocyte Growth Factor	RECIST	Response Evaluation Criteria in Solid Tumors
ICF	Informed Consent Form	SBRT	Stereotactic Body Radiation Therapy

1. OBJECTIVE

The overall objective of this study is to determine the safety and efficacy of combined immune checkpoint inhibitors and radiation therapy in metastatic non-small cell lung cancer patients.

1.1. Primary Objective

To determine the best overall response rate (ORR) (complete and partial), as measured on follow-up CT or PET/CT imaging after initiation of radiation therapy.

1.2. Secondary Objective(s)

To determine 1-year progression-free survival (PFS); 1-year overall survival (OS); safety/toxicity using CTCAE v4.0 until 30 days after the last dose of immune therapy or until the patient begins a new cancer-directed therapy, or death, whichever comes first; quality of life using FACT-L and FACIT Fatigue Scale at 3 month intervals until the time of systemic disease progression. In order to determine factors predictive of response to therapy, we will correlate the presence of response with radiotherapy variables (biologic effective dose, number of fractions, duration of radiotherapy, sequence of radiation and immune therapy), tumor variables (irradiated tumor site, size, histology, PD-L1 status, local response, extent of prior chemotherapy use), and patient variables (age, smoking status, and biologic correlates).

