5.2. Standard of Care Immune Checkpoint Inhibitors

Immune checkpoint inhibitors that are FDA approved for use in patients with metastatic NSCLC will be acceptable for use concurrently with radiotherapy in this trial. The choice of agents will be at the treating medical oncologist's discretion, and include:

- Nivolumab 240 mg once every 2 weeks (14 day cycle) or 480 mg once every 4 weeks (28 day cycle)
- Pembrolizumab 200 mg once every 3 weeks (21 day cycle)
- Atezolizumab 1200 mg once every 3 weeks (21 day cycle)

These agents should be continued per standard of care until either disease progression or unacceptable toxicity. In the case of Pembrolizumab, it is also recommended that patients should be on the drug for no more than 24 months even if there is no evidence of disease progression. Pembrolizumab may also be used in combination with Pemetrexed and Carboplatin for the first-line treatment of metastatic non-squamous NSCLC. If any of the immune therapy agents are permanently discontinued at any point, a final course of radiation therapy should be offered to the patient before switching to an alternative therapy. While the patient is receiving immune therapy, no other investigational or commercial agents or therapies may be administered with the intent to treat the subject's malignancy.

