13.3. Methods for Analysis

Data will be summarized with respect to baseline characteristics and safety measurements using descriptive statistics (quantitative data) and contingency tables (qualitative data). The safety analysis will consist of AE summaries (frequency tables based on CTCAE grades) and laboratory abnormalities summary. For the primary endpoint, the response rate and its 95% confidence interval will be estimated with a binomial distribution. Univariate and multivariate logistic regression model will be used to assess the association between response and several radiotherapy variables (biologic effective dose,

number of lesions treated, sequence of radiation and immune therapy), tumor variables (irradiated tumor site, size, growth rate, histology, PD-L1 status, local response, extent of prior chemotherapy use, and biologic correlates), and patient variables (age, smoking status, and other factors associated with secondary immunodeficiency). A predictive nomogram for response will be developed based on the outcome of the multivariate analysis. In the data analysis on the secondary endpoints, the Kaplan-Meier method will be used to estimate overall survival and progression-free survival. Wilcoxon signed-rank test for paired data will be used to assess the change of quality of life scores between two visits. Since the lung cancer score (LCS) of the FACT-L focuses on lung cancer symptoms, this will be used for the primary QOL endpoint; however, the more general subscales of physical and functional well-being on the Trial Outcome Index (FACT-TOI) will also be collected. A difference of 3 LCS points will be considered clinically significant.¹²⁻¹³ Where applicable, comparison will be made to previous randomized trials assessing immune checkpoint inhibitors alone in a comparable patient population.

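### The response-predictor model has no term for concurrent chemotherapy, so if any patients receive it, part of its effect can pass to histology and prior chemotherapy and into the nomogram

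*Combined protocol and SAP*

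**What the plan says.** Section 5.2 leaves the checkpoint inhibitor to the treating oncologist and adds: "Pembrolizumab may also be used in combination with Pemetrexed and Carboplatin for the first-line treatment of metastatic non-squamous NSCLC". Eligibility (4.1) restricts neither line of therapy nor histology, so combination-treated and checkpoint-only patients can both be enrolled.

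Section 13.3 is the operative text for the model: "Univariate and multivariate logistic regression model will be used to assess the association between response and several radiotherapy variables". Its radiotherapy list, after biologic effective dose, has "number of lesions treated, sequence of radiation and immune therapy". Its list for the tumour reads "tumor variables (irradiated tumor site, size, growth rate, histology, PD-L1 status, local response, extent of prior chemotherapy use, and biologic correlates". The third list, on the patient, is shorter and open-ended: "patient variables (age, smoking status, and other factors associated with secondary immunodeficiency".

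Section 1.2 gives the same kind of list among the objectives, for the tumour as follows: "tumor variables (irradiated tumor site, size, histology, PD-L1 status, local response, extent of prior chemotherapy use". The lists in the synopsis and 1.2 differ in detail from 13.3, but both contain histology and extent of prior chemotherapy. No list contains concurrent chemotherapy, the checkpoint agent or the regimen.

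Section 13.3 then goes further: "A predictive nomogram for response will be developed based on the outcome of the multivariate analysis". Nothing in the documents stratifies the model by regimen or sets combination-treated patients aside.

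**The concern.** Line of therapy and histology are the two conditions that 5.2 attaches to the chemotherapy combination. Both have a counterpart in the model, while the treatment they open the way to does not. That is the setting for omitted-variable confounding: an active co-treatment tied by the protocol itself to two included predictors.

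At stake is the objective in 1.2 of finding factors that predict response. The model could report non-squamous histology or little prior chemotherapy as favourable, and the nomogram could score patients on them, when a second anticancer treatment produced the difference.

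**Working it through.** **The plan's own figure.** The documents give no sample-size figure for the predictor model; it inherits N = 33. An exact search for the Simon minimax design (20% vs 40%, alpha 0.05, power 80%) returns 18 then 33 patients, with cut-offs of 4 and 10 responses, alpha 0.046, power 0.801 and early-termination probability 0.716. So 33 and 0.72 reproduce. (How 13.2 words the stage 1 stop is a separate matter.) At 20-40% response the model has 0.20 × 33 = 6.6 to 0.40 × 33 = 13.2, or about 7 to 13, responders. Section 13.3 lists 14 items (3 radiotherapy, 8 tumour, 3 patient), some of them groups of variables.

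**Inputs for the bias.**
- From the documents: response of 20% without chemotherapy (the null in 13.2); chemotherapy only in patients who are non-squamous and without prior chemotherapy (my reading of first-line in 5.2).
- Assumed, as the documents give no figure: 70% non-squamous; 50% with prior chemotherapy, independent of histology; 40% response with chemotherapy; uptake u of 25%, 50% or 80% among those who could receive it. Histology and prior chemotherapy have no true effect (odds ratio 1.00).

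**Formulas.**
- Response in the non-squamous, no-prior cell: c = 0.20 + u × (0.40 − 0.20). All other cells: 0.20 (odds 0.25).
- Non-squamous response: 0.5c + 0.5 × 0.20.
- Response without prior chemotherapy: 0.7c + 0.3 × 0.20.
- Combination-treated patients: 33 × 0.70 × 0.50 × u.

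For u = 50%: c = 0.30. Non-squamous response is 0.25, so the crude odds ratio is (0.25/0.75)/0.25 = 1.33. Response without prior chemotherapy is 0.27, so the odds ratio for prior chemotherapy is 0.25/(0.27/0.73) = 0.68.

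The planned model holds both terms at once. Its large-sample limit, from a logistic fit to the expected cell counts, is:

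| Uptake | Combination patients of 33 | Crude OR, non-squamous | Crude OR, prior chemo | Multivariate OR, non-squamous | Multivariate OR, prior chemo |
|---|---|---|---|---|---|
| 0% | 0 | 1.00 | 1.00 | 1.00 | 1.00 |
| 25% | 2.9 | 1.16 | 0.81 | 1.16 | 0.81 |
| 50% | 5.8 | 1.33 | 0.68 | 1.34 | 0.68 |
| 80% | 9.2 | 1.56 | 0.55 | 1.57 | 0.55 |

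With a concurrent-chemotherapy term, histology and prior chemotherapy return to 1.00 and chemotherapy takes its own odds ratio, (0.40/0.60)/(0.20/0.80) = 2.67.

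**Sensitivity.** With 55% response on the combination and 80% uptake, the pair becomes 2.13 and 0.37. If, in addition, only 30% have prior chemotherapy, it becomes 2.71 and 0.37.

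**At N = 33.** In simulated trials with the same assumed mix, the standard error of the histology log odds ratio is about 0.97, so a 95% interval spans a factor of exp(1.96 × 0.97) = 6.7 either way. At 40% response on the combination, histology was falsely significant in about 1-2% of trials and prior chemotherapy in about 2-6%. Adding the chemotherapy term to an ordinary logistic model made the fit fail in about 32-54% of trials, against 14-16% without it.

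**The case against.** **There may be little or no chemotherapy.** Section 2.2 describes these agents as approved in second line and beyond, and 5.2 also bars other commercial anticancer agents during immune therapy. At zero uptake the bias is nil. This stands as a limit on size. But 5.2 names the combination expressly, so the analysis should provide for it.

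**The analysis is modest in aim.** The synopsis calls it exploratory, and the text speaks of correlation and association rather than cause. This lowers the stakes. However, 1.2 places it under secondary objectives, and a nomogram is meant for prediction.

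**Thirty-three patients cannot show it either way.** Largely true. False significance for histology is rare, and the extra term strains a model that is already overloaded. That bears on how the term is fitted. It does not make the omission harmless, because the point estimates that would feed the nomogram are still shifted.

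**An open-ended item covers it.** Section 13.3 ends the patient list with unspecified factors linked to secondary immunodeficiency. That item does not name chemotherapy or regimen.

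**Stronger readings that the documents do not support.**
- A reader might infer that all of the chemotherapy effect will land on histology and prior chemotherapy. Other correlated terms, such as PD-L1 status, could take some.
- A reader might take a crude histology odds ratio as high as 2.8, from 70% of all non-squamous patients on the combination with 50% response: 0.20 + 0.7 × 0.30 = 0.41, and (0.41/0.59)/0.25 = 2.78. Only first-line patients qualify, so with 50% prior chemotherapy the share cannot exceed 50%, and no passage supports 70%. Nor may crude odds ratios for histology and prior chemotherapy be counted as two separate biases; they are two views of one effect.
- A reader might extend the point to the primary conclusion. The decision rule counts responders and makes no use of this model.

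**Conclusion.** The point holds as a conditional one. As written, the predictor model and nomogram confound a permitted active co-treatment with two listed predictors, and this bites only if some patients receive the combination.

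Under the central assumptions and 25-80% uptake, the spurious odds ratios are 1.16-1.57 for non-squamous histology and 0.81-0.55 for prior chemotherapy; larger values need several assumptions stacked together. Uptake, effect and case mix are all assumed. At N = 33 the practical risk is a shifted estimate carried into the nomogram more than a falsely significant histology result. The gap is worth closing because it is specific and cheap to close.

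**What to change.** 1. In 13.3, and to match in the synopsis and 1.2, add to the candidate predictors: systemic regimen at start (checkpoint inhibitor alone versus with pemetrexed-carboplatin). Dropping number of fractions or duration of radiotherapy to hold the count would not work in 13.3, which lists neither.
2. Record the regimen in its own case report form field. Footnote 12 of the study calendar names immune therapy only, 10.1.2 records no specific data from infusion visits, and the concomitant-medication assessment does not name chemotherapy.
3. Because the data are sparse, fit the term with a penalised (Firth) logistic model, or refit the model and nomogram without combination-treated patients as a sensitivity analysis.
4. State that histology and prior chemotherapy will not be interpreted, nor the nomogram built, without this.
5. Reconcile the two sentences in 5.2, one permitting the combination and one barring other commercial anticancer agents during immune therapy.

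Cost: one more data field, and a less precise model with wider intervals for histology and prior chemotherapy. The sample size and primary decision rule do not change.

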1.3. Correlative Objective(s)

Peripheral blood samples will be collected before initiation of radiation therapy, at the time of the first reimaging study, and with each subsequent change in response status to assess levels of circulating CD4+, CD8+ and Treg T-cell subsets, iNOS+/CD80+ macrophages, cytokines (HGF, TGF- β) and chemokines (CCL2, CXCL9, CXCL10, CXCL11). We will also determine changes of the circulating T-cells immune-repertoire (i-repertoire) by performing next generation sequencing of the CDR3 region of the T-cell receptor (TCR).

2. BACKGROUND

2.1. Background of Study Disease

An estimated 221,000 new cases of lung cancer were diagnosed in 2015, making it the second most common malignancy in men and women. It is also the leading cause of cancer death in the United States.¹ Non-small cell lung cancer (NSCLC) accounts for approximately three-fourths of new lung cancer diagnoses, the majority of which are locally advanced or metastatic at presentation. Patients with metastatic NSCLC often decline relatively rapidly, with one-year overall survival on the order of only 15-20%.²

2.2. Checkpoint Inhibitor Immune therapy for Stage IV NSCLC

The immune system normally functions to prevent and fight against invasive organisms and diseases. However, a dysregulated immune response can also be detrimental in the form of autoimmunity or excessive inflammation. As such, several immune checkpoints

have evolved in order to maintain homeostasis. Cancer has been shown to co-opt these checkpoints, leading to immune tolerance and subsequent progression of malignancy.³⁻⁵ In recent years immune checkpoint inhibitors have emerged as a novel therapy for a variety of human malignancies.⁶⁻¹¹ One well characterized checkpoint being targeted in metastatic NSCLC clinical trials is PD-1/PD-L1, with monoclonal antagonist antibody pharmaceuticals, such as Nivolumab, Pembrolizumab, and Atezolizumab, resulting in response rates of 19-25% and median response duration of 12.5-17.0 months.⁸⁻¹¹ To date, Nivolumab, Pembrolizumab, and Atezolizumab have been approved by the U.S. Food and Drug Administration for treatment of advanced NSCLC in second line therapy and beyond. Promising clinical outcome data continue to emerge from clinical trial studies suggesting activities of PD-1 blockade in small cell lung cancer (SCLC) and mesothelioma as well.

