13.2. Sample Size/Accrual Rate

The primary analysis will be for patients enrolled at time-points (A) and (B) above, whereas patients enrolled at time-point (C) will be included in observational analysis only (see section 3.1). The primary endpoint of this study is the overall response rate (complete + partial response) and the efficacy will be assessed using the Simon's two-stage Minmax design. A sample size of 33 patients is chosen to differentiate between the response rate of 20% and 40% with 80% power at a significance level of 0.05. In particular, 18 patients will be enrolled at the first stage. If 15 or more of the first 18 patients have disease progression prior to any response, the trial will be terminated; otherwise an additional 15 patients will be treated for a total of 33 patients. In the final data analysis, if 10 or fewer patients respond among 33 patients, the treatment will be concluded ineffective. The probability of early termination due to futility is 0.72.

For correlative study between biomarkers and response, this sample size will have at least 80% power to detect a 50% change/difference on biomarker data between response and non-response groups using a two-sided two-sample t-test at 0.05 significance level, assuming that the response rate is 35% or higher and the coefficient of variation (CV) of biomarkers is 0.45.

Approximately 100 patients with metastatic NSCLC are diagnosed and treated each year at our institution, many of whom will be candidates for immune checkpoint therapy. As such, we expect to accrue 3 patients per month to this trial for an estimated accrual period of one year. The full estimated duration of the study is two years.

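### One 11/33 rule against a 20% null covers both checkpoint monotherapy and first-line pembrolizumab plus chemotherapy, so a positive pooled result cannot by itself show that radiation improves on checkpoint inhibitors alone

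*Combined protocol and SAP*

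**What the plan says.** Section 2.3 hypothesises higher response rates than earlier studies of checkpoint inhibitors used alone. Section 3.1 describes a non-randomized phase II trial, so the null rate has to stand in for a control arm.

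The only figure for that comparison is in Section 2.2, which describes the PD-1/PD-L1 agents as "resulting in response rates of 19-25" percent. The sentence after it says that these agents are approved in the second line and beyond.

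Section 13.2 sets the design: "A sample size of 33 patients is chosen to differentiate between the response rate of 20% and 40% with 80% power". It needs at least 11 responses in 33 and quotes a 0.72 probability of early termination. It does not say where the 20% comes from. Its only limit on the primary analysis set concerns time of enrolment, not regimen.

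Section 5.2 leaves the agent to the treating oncologist and adds: "Pembrolizumab may also be used in combination with Pemetrexed and Carboplatin for the first-line treatment of metastatic non-squamous NSCLC". Section 4.1 does not restrict line of therapy.

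Section 13.3 plans a logistic regression of response. Its covariates include extent of prior chemotherapy, histology and PD-L1 status, but not concurrent chemotherapy or regimen. It closes by saying that, where applicable, "comparison will be made to previous randomized trials assessing immune checkpoint inhibitors alone in a comparable patient population".

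**The concern.** The benchmark describes checkpoint inhibitors without chemotherapy, while the enrolled population may include patients who receive two cytotoxic drugs at the same time. Scoring only non-irradiated lesions (Sections 11.1.2 and 11.2) keeps the local effect of radiation out of the endpoint. It does not keep out systemic chemotherapy, which acts on those same lesions.

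Two things follow. First, the stated 0.05 level may fail within the protocol's own 19-25% range, even if every patient receives monotherapy. Second, each chemo-combination patient moves the background rate toward whatever that regimen achieves without radiation, and the rule does not adjust. A trial that reaches 11/33 could then be read as evidence for radiation when regimen mix produced the result.

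**Working it through.** **Inputs from Section 13.2.** Null 20%, target 40%, level 0.05 (taken as one-sided, as is usual for a Simon design), power 80%, n1 = 18, N = 33, success at 11 or more responses. The stage 1 bound r1 is taken first as 4, because that value reproduces the quoted 0.72.

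**Formulas.** With b(x; n, p) the binomial probability:
- PET(p) = sum of b(x; 18, p) for x = 0 to r1.
- P(declare effective | p) = sum over x = r1+1 to 18 of b(x; 18, p) × P(Y ≥ 11 − x), with Y ~ Bin(15, p).

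**The plan's own figures.** An exhaustive minimax search for 20% against 40% (level at most 0.05, power at least 0.80) returns r1/n1 = 4/18 and r/N = 10/33. That design has PET(0.20) = 0.716, error 0.0458 and power 0.801. The stated design reproduces with r1 = 4. The written stage 1 rule (15 or more of 18 progressing before any response), read as 3 or fewer responses, gives PET 0.501, error 0.0497 and power 0.825. Both readings are carried below.

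**Background rates in the protocol's own range, no radiation effect.**

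| True rate without radiation effect | P(declare effective), r1 = 4 | r1 = 3 |
|---|---|---|
| 19% | 0.033 | 0.036 |
| 20% | 0.046 | 0.050 |
| 22% | 0.082 | 0.089 |
| 25% | 0.166 | 0.178 |

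With r1 = 4 the probability reaches 0.05 at a true rate of about 20.3%. At 25% it is 0.166 / 0.05 = 3.3 times the stated level.

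**Regimen mix (assumption).** The documents give neither the share f of patients on pembrolizumab plus chemotherapy nor that regimen's response rate q without radiation. Taking 20% on monotherapy, the blended rate is p = (1 − f) × 0.20 + f × q. Results use r1 = 4.

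| f | q | Blended p | P(declare effective) |
|---|---|---|---|
| 25% | 30% | 0.225 | 0.09 |
| 25% | 40% | 0.250 | 0.17 |
| 25% | 50% | 0.275 | 0.26 |
| 50% | 30% | 0.250 | 0.17 |
| 50% | 40% | 0.300 | 0.37 |
| 50% | 50% | 0.350 | 0.61 |

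**Power in a monotherapy subset.** If half the sample is on the combination, about 16 patients remain (33/2 = 16.5). A one-sided exact 5% test then needs 7 of 16 against 20%, since P(X ≥ 7 | 0.20) = 0.027, or 8 of 16 against 25%, since P(X ≥ 8 | 0.25) = 0.027. At a true rate of 40%, power is about 0.47 and 0.28 respectively.

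**The case against.** Choosing a null inside a historical range is a judgement, and every single-arm design is sensitive to it. Section 3.1 openly chooses a non-randomized phase II because prospective data are limited. That stands, and it is why the remedy is disclosure and a narrower claim rather than a redesign.

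Four stronger readings are tempting, and the documents do not support them:

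- A reader might infer that the 0.05 level holds only at exactly 20%. With r1 = 4 it holds at 19%, at 20% and up to about 20.3%.
- A reader might take the 20% as documented second-line monotherapy data. Section 13.2 gives no source, and Section 2.2 attaches the line of therapy to the approval sentence, not to the range. The link is an inference, though no other benchmark is given.
- A reader might conclude that the analysis ignores these patients altogether. Prior chemotherapy is a partial proxy for line, histology bears on who can receive a non-squamous regimen, and the closing comparison is limited to a comparable population. But concurrent chemotherapy is not a covariate, and none of these terms changes the 11/33 rule.
- A reader might treat the 0.09-0.61 figures as the trial's error rate. They rest on assumed shares and response rates.

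**Conclusion.** The concern stands in a limited form. On the protocol's own figures, the probability of declaring efficacy with no radiation effect runs from 0.033 at 19% to 0.166 at 25% (0.178 at 25% if stage 1 stops at 3 or fewer responses). These values need no outside data, only the inference that 19-25% is the relevant background, and they apply even if nobody receives chemotherapy.

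The regimen problem is established in direction, provided that the combination has a higher background response rate than monotherapy. Its size is not established: 0.09-0.26 with a quarter of patients on the combination and 0.17-0.61 with half, under assumed rates of 30-50%. The documents do not show that the trial would succeed through case mix. They show that, as written, the pooled rule cannot separate that explanation from a radiation effect.

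**What to change.** In Section 13.2:
- Reconcile the written stage 1 rule with the stated 0.72, then state the false-positive rate across 19-25% for the reconciled rule.
- Give the source of the 20%.
- State that the pooled 11/33 result does not by itself support a claim that radiation improves on checkpoint inhibitors alone.

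In Section 13.3:
- Pre-specify response rates with exact intervals separately for checkpoint monotherapy and for pembrolizumab plus chemotherapy, and by line of therapy.
- Base any claim of improvement over checkpoint inhibitors alone, and the external comparison in the last sentence, on monotherapy patients only, against both 20% and 25%.

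The cost is wording and one table, with no extra patients. The downsides should be stated openly: the published error rate becomes less favourable, and the monotherapy subset may be too small for a firm conclusion (power about 0.47 or 0.28 in the 16-patient example). Raising the pooled bar instead would also cost power. With r1 = 4, requiring 13 of 33 brings the error to 0.047 at a 25% background, but power at 40% falls to 0.59, and chemotherapy patients would still be in the count.
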